15.2 Statistical and Data Analysis

Availability of case and justification of sample size. According to our co-investigator and breast pathologist, the surgeons at our cancer center operated 24 cases of DCIS in 2013.

Ages	# of patients at UT Health San Antonio Mays Cancer Center
< 50	7
50-59	10
> 60	7

We consider about 60-70% enrollment in 5-year recruitment duration, we shall be able to recruit about 50-60 patients with menopausal status clinically confirmed. Tissue from this study will be compared to DCIS specimens from patients not treated with rapamycin. These specimens will be collected through the ongoing biorepository.

Statistically significant differences of the histopathological parameters and the molecular markers between the core biopsy and surgical specimens due to the rapamycin treatment will be tested by Mantel-Haenszel test for categorical data with scores ranging from 0 to 4 (or higher) as shown in Figure 2. To reach statistical power >70%, a patient group size of 24 or more is required for us to detect the difference of a score of 0.3 between untreated biopsy and treated surgical specimens with the P value targeted at 0.05 for one-sided Mantel-Haenszel test.

The **Mantel-Haenszel test** (between Rapamycin treatment & non-participant patients) will be set up as follows.

No Rapamycin # of patients (c) # of patients (d) c/(c+d)

Test between treatment & non-participant patients				
Study		IHC score ≤ 2	IHC score > 2	Percentage
UT Health San Antonio	Rapamycin	<pre># of patients (a)</pre>	# of patients (b)	a/(a+b)

Mantel-Haenszel test will allow us to extend IHC score to full range (instead of dichotomizing the IHC score), as well as other sites if more patients will be enrolled at different sites (we will not lump all patients together into one group, in case the underlying population demographic is a concern at different enrollment sites). Significance will be determined at p-value < 0.05 (Chi-square distributed with one degree of freedom). During the recruitment period, we will monitor the IHC scores different from two groups (treated/untreated) with simple *t* test on average IHC score (across all patients within each group) for each marker, in order to assess the IHC effectiveness, enrollment progress and patient demographic parameters and their association to final study outcomes.

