For statistical test within either treatment or control arm, we will use **McNemar's test** to examine IHC score differences between biopsy and surgical tissues (at significance level of 0.05). The 2x2 table set up as follows.

Test within treatment or no treatment

After treatment

		IHC score ≤ 2	IHC score > 2
Before treatment	IHC score ≤ 2	# of patients with	# of patients with
		lower IHC scores before & after	higher IHC score after treatment
	IHC score > 2	# of patients with	# of patients with
		lower IHC score after treatment	higher IHC scores before & after

Similar to between arm test, during the recruitment period, we will monitor the IHC scores different within each arm with simple paired-*t* test on average IHC score difference for each marker, in order to assess the IHC effectiveness, enrollment progress and patient demographic parameters and their association to final study outcomes.

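### Section 15.2 words its only power figure (>70% at n = 24) for Mantel-Haenszel on full scores, but gives biopsy versus surgery to McNemar's test cut at 2, to which that figure does not carry over

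*Combined protocol and SAP*

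**What the plan says.** All of this is in Section 15.2 of the combined protocol and SAP.

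- **First assignment.** Differences between core biopsy and surgical specimen, for histopathological parameters and molecular markers, "will be tested by Mantel-Haenszel test for categorical data with scores ranging from 0 to 4" (or higher).
- **Power.** For power above 70%, "a patient group size of 24 or more is required for us to detect the difference of a score of 0.3". The difference is specified as one "between untreated biopsy and treated surgical specimens with the P value targeted at 0.05 for one-sided Mantel-Haenszel test". No SD, score distribution or pairing rule is given, and no other power figure appears.
- **Between-group layout.** Mantel-Haenszel is then set out for a different contrast: "between Rapamycin treatment & non-participant patients) will be set up as follows". The printed table is cut at 2 or below versus above 2. The text adds: "Mantel-Haenszel test will allow us to extend IHC score to full range (instead of dichotomizing the IHC score". The decision rule in that paragraph is: "Significance will be determined at p-value < 0.05 (Chi-square distributed with one degree of freedom".
- **Within-arm layout.** "For statistical test within either treatment or control arm, we will use" McNemar's test, applied to IHC scores at biopsy and surgery, with the same cut and a 0.05 level. Neither a sidedness nor a power is stated.
- **Accrual.** "we shall be able to recruit about 50-60 patients with menopausal status clinically confirmed".

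Section 4.1 makes reduction of malignant markers in treated patients a primary objective. The biopsy-to-surgery change in IHC score bears directly on it.

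**The concern.** The text supports two readings, and each leaves a gap.

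1. **Both tests apply to biopsy versus surgery.** For IHC scores there are then two tests that can disagree on the same patients. Neither is named as deciding, so the choice stays open until data are seen. The section also plans t tests on these scores during recruitment.
2. **The layouts govern:** Mantel-Haenszel between groups, McNemar within arm. No two tests then compete. However, the only power sentence is worded for biopsy versus surgery and attached to a test not used for that contrast, and the within-patient test has no sample-size support.

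Sidedness is unsettled as well. The power is one-sided, McNemar's 0.05 has no stated side, and the chi-square rule with one degree of freedom sits in the between-group paragraph and may govern only that contrast.

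**Working it through.** **Step 1: the plan's own figure.** It cannot be reproduced, because the inputs are not stated. Solving backwards for 70% power at n = 24, one-sided 0.05 (z = 1.645 + 0.524 = 2.169, normal approximation):

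- Paired mean shift: SD of change = 0.3 × √24 / 2.169 = 0.68.
- Two independent groups of 24: SD = 0.3 × √12 / 2.169 = 0.48 per group.
- 0.3 read as a difference in proportions, 0.2 versus 0.5: n = [1.645 × √(2 × 0.35 × 0.65) + 0.524 × √(0.16 + 0.25)]² / 0.3² = 23.2, so 24 per group.

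The stated figure is therefore attainable on several readings. None of them is a McNemar calculation.

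**Step 2: why it does not transfer.** McNemar's statistic uses only patients who cross from above 2 to 2 or below, or the reverse. A fall from 4 to 3 or from 2 to 1 counts as no change. A mean shift of 0.3 does not fix how many patients cross.

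**Step 3: illustration.** These assumptions are ours, not the plan's:

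- 0.3 is a mean paired shift, and all moves are one category.
- 40% fall and 10% rise, at the same rates at every score. This is a simplification at the ends of the scale.
- Mean change = 0.10 − 0.40 = −0.30; SD = √(0.40 + 0.10 − 0.30²) = 0.64.
- 20% of biopsies are at score 2; n = 24; one-sided 0.05.

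Full-score matched test: z = (falls − rises)/√(falls + rises) over all changers. With one-category moves, the patient-matched Mantel-Haenszel mean-score test and the Wilcoxon signed-rank test both reduce to this. McNemar uses the same z over crossers only, with P(down) = share at score 3 × 0.40 and P(up) = 0.20 × 0.10 = 0.02. The exact version of each uses the binomial with probability ½. Power is the sum over all possible numbers of downs and ups.

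| Test, n = 24, one-sided | P(down) / P(up) | Expected changers or crossers | Uncorrected asymptotic | Exact |
|---|---|---|---|---|
| Full-score matched | 0.40 / 0.10 | 12.0 | 72% | 59% |
| McNemar, 20% at score 3 | 0.08 / 0.02 | 2.4 | 20% | 3% |
| McNemar, 40% at score 3 | 0.16 / 0.02 | 4.3 | 53% | 24% |
| McNemar, 50% at score 3 | 0.20 / 0.02 | 5.3 | 66% | 40% |

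**Step 4: why the variant matters.** With so few crossers the two versions reject at different points. Uncorrected, three crossers all downward suffice (√3 = 1.73 > 1.645). The exact test needs at least five (0.5⁴ = 0.063; 0.5⁵ = 0.031). Section 15.2 does not say which version is meant.

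**The case against.** The best defence is that the layouts give one test to each contrast, so nothing competes and only a sentence is misplaced. That is a fair reading, and it limits the claim of an open choice to the first reading. It does not rescue the power figure, which then supports no within-patient test.

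A second defence is that Mantel-Haenszel matched on patient and applied to the printed cut is McNemar's statistic without continuity correction, so the two tests may be one. That is true of the algebra. But the power sentence speaks of a score difference of 0.3 on a scale of 0 to 4 or higher, and the section mentions strata only for enrolment sites. The real contrast is full score against dichotomised score.

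Third, the illustration rests on assumed inputs and on reading 0.3 as a mean paired shift. If 0.3 was meant as a difference in proportions, the percentages describe a quantity the plan did not power. This stands, and the percentages should be read only as showing sensitivity.

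A reader might also infer that McNemar is always the weaker test, or that it is adequate once about half the biopsies score 3. The documents support neither. With 60% at score 3, uncorrected McNemar gives 76% against 72% for the full-score test, while the exact versions give 56% against 59%. With 50% at score 3, even the uncorrected one-sided test gives only 66%.

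**Conclusion.** The point holds. The section's only power figure is worded for Mantel-Haenszel on full scores, and on either reading it does not describe McNemar's test cut at 2. That conclusion comes from the text and needs no assumed numbers. It concerns IHC scores only, since McNemar is not assigned to the other histopathological parameters.

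The size of any shortfall cannot be fixed. It depends on the distribution of biopsy scores, the sidedness and the test variant, none of which the plan states. Under the single illustrative case, McNemar's one-sided power at n = 24 runs from 3% to 66%, against 59% to 72% for a full-score matched test.

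A reader might go further and conclude that the >70% is wrong or that the trial is underpowered. The documents do not support this: the figure is attainable if the SD of paired change is about 0.68 or less (normal approximation), and recruitment of more than 24 is expected. This should be fixed before analysis, but it does not invalidate the design.

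**What to change.** In Section 15.2:

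1. Name one deciding within-patient test on the full score, either the patient-matched Mantel-Haenszel mean-score test or the Wilcoxon signed-rank test. Keep the McNemar table as supportive.
2. Say which contrast the between-group Mantel-Haenszel test serves, and whether it uses the cut or the full score.
3. State one sidedness for each contrast, and use it in both the power text and the analysis text.
4. Restate the power for the deciding within-patient test with its assumed SD of paired change and its variant (asymptotic or exact). Give it at n = 24 and at the expected number of efficacy-evaluable patients. The 50-60 recruited is an upper limit for that number, because Section 6 restricts efficacy evaluation to patients who complete a minimum course and have surgery within the window.

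The cost is wording and a short recalculation, with no extra patients or data. The stated power may become less favourable, and the full-score test is not stronger under every score distribution. Retaining McNemar as the deciding test would also close the gap, provided its sidedness, variant, assumed crossing rates and power were stated. The full score is preferred because it uses every change and is the scale on which the 0.3 difference is expressed.

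### Section 15.2 gives biopsy versus surgery two conflicting tests with neither named as deciding, and its only power statement (one-sided 0.05) does not match its only Mantel-Haenszel decision rule (1-df chi-square at 0.05)

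*Combined protocol and SAP*

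**What the plan says.** All the relevant text is in section 15.2.

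- **Biopsy versus surgery, first description.** Differences between core biopsy and surgical specimen "will be tested by Mantel-Haenszel test for categorical data with scores ranging from 0 to 4 (or higher".
- **Power.** The target is power above 70%, and the plan states that "a patient group size of 24 or more is required for us to detect the difference of a score of 0.3". The contrast is each patient's biopsy before treatment against the surgical tissue after it. The level is given separately as a "P value targeted at 0.05 for one-sided Mantel-Haenszel test". There is no other power statement.
- **Mantel-Haenszel set-up.** The test laid out next is ("between Rapamycin treatment & non-participant patients) will be set up as follows"). Its table cuts the IHC score at 2, with the remark that "Mantel-Haenszel test will allow us to extend IHC score to full range (instead of dichotomizing the IHC score"). The decision rule is "Significance will be determined at p-value < 0.05 (Chi-square distributed with one degree of freedom"). Nothing is said about halving the p-value or taking a signed root.
- **Biopsy versus surgery, second description.** A later sentence opens "For statistical test within either treatment or control arm, we will use", and the method it names is that of McNemar. The stated purpose is "to examine IHC score differences between biopsy and surgical tissues (at significance level of 0.05"). Its table again cuts the score at 2, and no sidedness is given.

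Section 4.1 makes reduction of malignant markers one of two primary objectives. No passage says which of these tests decides it. The t and paired-t tests in section 15.2 are described for monitoring during recruitment, so they are not counted here as competing final analyses.

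**The concern.** There are two separate conflicts.

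First, one contrast (biopsy versus surgery) has two tests on two scorings. One uses the ordered score and the other records only whether the score crosses 2. They can disagree on the same data, and with no order of precedence the choice could be made after the results are seen.

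Second, the power statement and the decision rule differ in contrast (within patient against between groups) and in sidedness (one-sided 0.05 against a statistic that ignores direction). A reader who takes the stated power as the power of the stated rule is mistaken, whichever way the chi-square sentence is read.

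At stake is whether a result on a primary objective can be called positive under a rule fixed in advance, and whether the quoted power describes that rule.

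**Working it through.** **1. Can the plan's own figure be reproduced?** Inputs from section 15.2: n = 24, difference 0.3, one-sided 0.05, power above 70%. The available text shows no SD or score distribution. The sentence on scores cites a Figure 2 that is not shown, and the only captioned Fig. 2 (section 3) is a mouse cell-sorting profile. The figure can therefore only be back-solved. On a paired-mean reading with power exactly 70%, z sum = 1.645 + 0.524 = 2.169, so the implied SD of the difference = 0.3 × √24 / 2.169 = 0.678.

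Another reading does return 24. Take 0.3 as a difference in proportions, for example 0.5 versus 0.8, with pooled proportion 0.65:

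n = [(1.645 × √(2 × 0.65 × 0.35) + 0.524 × √(0.25 + 0.16)) / 0.3]² = 23.2, so 24 per group, with 71.3% power.

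The text speaks of a score and gives no rates, so this is a possible origin, not a confirmation.

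**2. The two cut-offs on a 1-df statistic.** One-sided 0.05: 1.645² = 2.706, which is p = 0.10 on the chi-square. Stated rule: 1.960² = 3.841, p = 0.05.

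**3. If the chi-square rule covers only treated versus non-participants.** No recalculation applies. The power statement concerns biopsy versus surgery, so the rule as set up has no power figure.

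**4. If the rule covers every Mantel-Haenszel test.** For biopsy versus surgery only, let P1 be the one-sided power at 24 and d = 1.645 + z(P1). Then power under the stated rule = Φ(d − 1.960), and n for 70% = 24 × ((1.960 + 0.524)/d)².

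| P1 (assumed) | d | Power at 24, stated rule | n for 70% |
|---|---|---|---|
| 70% | 2.169 | 58% | 31.5, so 32 |
| 75% | 2.319 | 64% | 27.5, so 28 |
| 80% | 2.486 | 70% | 24.0, so 24 |
| 90% | 2.926 | 83% | 17.3, so 18 |

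Break-even is P1 = Φ(1.960 + 0.524 − 1.645) = 0.799. With the forecast 50-60 patients, if all are evaluable pairs and the 70% row is used: Φ(2.169 × √(50/24) − 1.960) = 0.879 and Φ(2.169 × √(60/24) − 1.960) = 0.929.

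These are normal approximations, conditional on the sponsor's figure.

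**5. The two scorings on the same data.** Constructed example: 24 pairs, 7 fall from 4 to 3 and 17 do not change, so the mean fall is 7/24 = 0.29, close to the 0.3 in the plan. McNemar at the cut of 2 has no discordant pair and shows no change. On the full-range scores with each patient as a stratum, the 1-df statistic is (sum of differences)² / (sum of squared differences) = 49/7 = 7.0, p = 0.008.

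Section 15.2 mentions strata only by enrolment site. Without patient strata the p-value depends on the 17 unchanged scores: about 0.005 if all are 4, 0.17 if all are 2 and 0.54 if all are 0. The example shows that the scorings can conflict; it does not measure how often.

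**The case against.** The strongest reply is that the chi-square sentence follows the treated-versus-non-participant table and governs only that test. There is then no clash of sidedness within one contrast, and 58% and 32 describe no analysis in the plan. This is a fair reading, and those two figures hold only on the other one. It does not rescue the text: the sole decision rule for Mantel-Haenszel then has no power behind it, and biopsy versus surgery still has two tests.

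A second reply is that this is a non-randomised, open-label phase II window study expecting 50-60 patients, so the loss from a two-sided rule is small. For biopsy versus surgery that largely stands (88-93% in the 70% case). Enrolment does not settle which test decides.

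Some stronger conclusions might be inferred and are not supported:

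- **That 24 is wrong or the trial is underpowered.** Without an SD or score distribution, the power above 70% can be neither confirmed nor refuted.
- **That 58% is the lowest possible power and 32 the largest number needed.** This holds only for biopsy versus surgery. For treated versus untreated, carrying over the implied SD with an assumed biopsy-surgery correlation r, two-sided power at 24 per group is Φ(2.169 × √(1 − r) − 1.960): 58% at r = 0, down to 22% at r = 0.7.
- **That the missing power figure and specimen number for the untreated group are a contradiction.** They are missing detail.

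**Conclusion.** The contradiction stands, on the text alone. Biopsy versus surgery is assigned both to Mantel-Haenszel on the full score and to McNemar at a cut of 2, with neither deciding. The only power statement and the only Mantel-Haenszel decision rule do not belong together: they differ in contrast, or, if the rule is read broadly, in sidedness for the same contrast.

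The effect on power is conditional and limited. It runs from none, if one-sided power at 24 is already about 80%, to a fall from 70% to about 58%, if it is exactly 70% and the rule covers biopsy versus surgery. At 50-60 evaluable pairs it is of little practical weight. The undecided choice between two scorings matters more, because it can change the conclusion on a primary objective whatever the enrolment. This should be corrected before analysis.

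**What to change.** In section 15.2:

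1. Name one deciding analysis for biopsy versus surgery, preferably a paired test on the full-range scores to which the power statement refers. Keep McNemar at the cut of 2 as supportive, and reserve Mantel-Haenszel for treated versus untreated.
2. Use the same sidedness in the power statement and the decision rule. Either test the signed root of the statistic at one-sided 0.05, with the expected direction stated for each marker (section 18 gives none for the autophagy and apoptosis markers), or keep the two-sided rule and restate the power from the sponsor's own SD or score distribution.
3. State that the power figure applies to biopsy versus surgery only and does not cover treated versus untreated.

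The cost is wording and one recalculation. A two-sided rule means a less favourable stated power at 24. A one-sided rule gives up claims in the opposite direction. Making McNemar supportive means that crossing the cut of 2 no longer decides the result. No extra patients are needed.

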4.1 Primary Objective

- 1. Reduction of MaSC in DCIS, LCIS, ALH or ADH in patients receiving rapamycin
- 2. Reduction of malignant markers in DCIS, LCIS, ALH or ADH in patients receiving rapamycin

4.2 Secondary Objectives

- 1. Toxicity
- 2. Surgical complications

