18. SAMPLES FOR BIOMARKER EVALUATION

Fresh tissue will be collected from patients with DCIS, LCIS, ALH or ADH treated with rapamycin. Tissue will be processed for IHC staining of p16, COX2, and Ki-67 in the core biopsy following the procedures described by Kerlikowske et al (66). We will also do IHC for autophagy markers, Beclin1 and LC3, and TUNEL assay to determine how rapamycin treatment may alter autophagy and apoptosis in the DCIS lesions.

To determine the effect of short-term rapamycin treatment on histopathological biomarkers in DCIS. A pathologist will quantify histopathological parameters including lesion size, nuclear grade, and presence of necrosis in each patient's surgical specimens, as well as IHC for the markers including p16, COX2, and Ki-67.

Three specific parameters will be evaluated:

- 1. Luminal-to-basal epithelial ratio, which will examine the MaSC in both luminal and basal cells, and their ratio, in order to address whether this ratio will change during aging;
- 2. Basal and luminal stem/progenitor cell frequency, which will examine the percentage of cells that are capable forming spheres, and whether these frequencies will change during aging; and
- 3. 3D structure regeneration frequency in serial passages, which will examine the selfrenewal/regeneration capacity of the stem and progenitor cells that are capable of forming spheres in suspension culture and in 3D-ECM culture, and can re-form the spheres when the sphere-forming cells are dissociated and allowed to regenerate spheres.

All fresh tissue specimens will be delivered to [name] laboratory located at:

UT Health San Antonio [name] [contact]

APPENDIX 1 – Common Toxicity Criteria for Adverse Events

Toxicity will be graded according to the NCI's Common Toxicity Criteria for Adverse Events (CTCAE) version 4.03. The CTCAE version 4.03 can be accessed at the following link: http://evs.nci.nih.gov/ftp1/CTCAE/CTCAE 4.03 2010-06-14 QuickReference 5x7.pdf

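### The malignant-markers primary objective names no lead marker and no lead contrast, while each IHC marker is tested at an unadjusted 0.05 both between groups and within arms

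*Combined protocol and SAP*

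**What the plan says.** Section 4.1 gives the second primary objective as "Reduction of malignant markers in DCIS, LCIS, ALH or ADH in patients receiving rapamycin". Neither that section nor the synopsis lists the markers.

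Section 18 names p16, COX2 and Ki-67 as an open list and adds "We will also do IHC for autophagy markers, Beclin1 and LC3, and TUNEL assay". It also lists lesion size, nuclear grade and necrosis. Nothing is ranked.

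Section 15.2 describes several tests:
- Mantel-Haenszel is first named for histopathological parameters and molecular markers, core biopsy against surgical specimen.
- Mantel-Haenszel is then tabulated for treated against non-participant patients, with the rule "Significance will be determined at p-value < 0.05 (Chi-square distributed with one degree of freedom".
- McNemar follows. That paragraph opens "For statistical test within either treatment or control arm" and uses the test "to examine IHC score differences between biopsy and surgical tissues (at significance level of 0.05".
- Per-marker t tests and paired t tests are run during recruitment, with no number of looks or alpha given.

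The sample-size statement reads "To reach statistical power >70%, a patient group size of 24 or more is required". The stated aim at that size: "detect the difference of a score of 0.3 between untreated biopsy and treated surgical specimens". The error level and sidedness are given separately: "with the P value targeted at 0.05 for one-sided Mantel-Haenszel test". The statement does not say which marker's score is meant and does not call that contrast primary.

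**The concern.** A declared primary objective needs one result, or a defined set with a rule, that settles it. Here each IHC marker gets its own 0.05 test between groups and another within each arm, and no text says which one answers the objective. A fall in one core marker on one contrast could be reported as success. A reader of the final report could not tell a planned answer from one selected afterwards, and the false-positive rate for the objective as a whole would exceed the nominal 5%.

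**Working it through.** **The plan's own figure.** The plan claims more than 70% power with 24 patients for a difference of 0.3 at one-sided 0.05. It states no SD, so this cannot be reproduced. Solving for the SD of the paired difference that gives exactly 70%:

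SD = 0.3 × √24 / (1.645 + 0.524) = 1.470 / 2.169 = 0.678

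This back-solved SD is an assumption carried into the power figures below.

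**Inputs for the error rate.**
- Alpha is 0.05 per test (section 15.2).
- There are 3 core markers (section 18).
- There are up to 3 contrasts per IHC marker: between groups, within the treated arm, within the control arm (section 15.2).
- There are 9 endpoints on biopsy versus surgery: the 3 core markers, Beclin1, LC3, TUNEL and 3 histopathological parameters. Section 15.2 assigns both histopathology and molecular markers to that comparison.

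**Chance of at least one p<0.05 with no effect, independent tests: 1 − 0.95^k.**

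| Set counted | k | Result |
|---|---|---|
| 3 core markers, 1 contrast | 3 | 14.3% |
| 3 core markers, 2 contrasts | 6 | 26.5% |
| 3 core markers, 3 contrasts | 9 | 37.0% |
| 9 endpoints, biopsy vs surgery only | 9 | 37.0% |

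**Effect of correlation.** With three tests equally correlated at 0.5, 14.3% falls to 12.4%. A simulation of the 1-df Mantel-Haenszel and McNemar tests was also run. It assumed 24 or 55 per arm, marker correlation 0, 0.3 or 0.6, biopsy-surgery correlation 0.5 and half of scores above 2. For the three core markers it gave 18% to 27% on two contrasts and 23% to 35% on three. Exact McNemar gives the lower values.

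**Direction.** The objective is a reduction, and a 1-df chi-square test is two-sided. A chance rejection in rapamycin's favour therefore has probability about 0.025 per test:
- 3 tests: 1 − 0.975^3 = 7.3%
- 6 tests: 1 − 0.975^6 = 14.1%

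If the one-sided 0.05 of the sample-size statement were the decision rule, the full 5% per test would lie in rapamycin's favour, and 14.3% and 26.5% would apply instead.

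**Power cost of Holm over three markers.** The strictest step is 0.05/3 = 0.0167, two-sided, with z = 2.394 in place of 1.960. The assumed SD of change is 0.678.
- Paired, within the treated arm, n=50: 0.3 × √50 / 0.678 = 3.13. Power is Φ(3.13 − 1.96) = 88%, falling to Φ(3.13 − 2.39) = 77%.
- Change in treated versus untreated, assumed 50 per group: 3.13 / √2 = 2.21. Power is Φ(2.21 − 1.96) = 60%, falling to Φ(2.21 − 2.39) = 43%.

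**The case against.** The strongest reply is that this is a small non-randomised window trial, that section 18 in effect identifies p16, COX2 and Ki-67 as the set, and that the sample-size sentence points to biopsy versus surgery. On that reading there are three tests, with a 14% chance of any false positive and about 7% in the favourable direction. This limits the size but does not remove the defect. The core list is open, the sample-size sentence does not call its contrast primary, and the first table set out after it is between groups. Early phase is no answer either, since the plan itself uses p<0.05 as its significance rule for a primary objective.

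A reader might infer something stronger: that a false positive is more likely than not, with figures such as 46% for 12 tests or 71% for 24. The documents do not support that. Those counts include the three MaSC parameters, which belong to the other primary objective and have no explicit test in section 15.2. They also apply tables written for IHC scores of at most 2 versus above 2 to endpoints that are not IHC scores. Under independence the chance passes one half only at 14 tests (51.2%; 13 give 48.7%).

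Nor does the text support reading any single positive as success. Section 18 gives Beclin1, LC3 and TUNEL a mechanistic purpose, and a change in an autophagy marker is not naturally a reduction of a malignant marker. A positive McNemar test in the control arm is likewise no claim for rapamycin, so the three-contrast figure is an upper count for the core markers.

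**Conclusion.** The point holds at moderate size. No lead marker, lead contrast or multiplicity rule is stated for a declared primary objective, and following the plan as written inflates its error rate. For the core markers the chance of at least one p<0.05 under no effect is about 14%, 26% or 37% for one, two or three contrasts, somewhat lower with correlation. It is 37% for the nine marker and histopathology endpoints on biopsy versus surgery alone. In rapamycin's favour only, under the two-sided rule, it is about 7% to 14% for three to six tests.

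The headline figures assume independent tests and no systematic difference between biopsy and surgical specimens or between the non-randomised groups; such a difference could raise the true rate. The recruitment-period t tests are not counted and would add to the figures if used for inference. The power figures rest on the back-solved SD and, for the between-group case, on an assumed control group of 50, because the plan gives neither.

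**What to change.** Before data are examined, add to section 15.2 one lead marker chosen from p16, COX2 and Ki-67, and one decisive contrast, tested at 0.05 with its sidedness stated. Alternatively, define the objective as those three markers and apply Holm at an overall 0.05 on that one contrast. Report the other contrast, Beclin1, LC3, TUNEL and histopathology as supportive or exploratory, with estimates and no significance claim.

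The change is a few sentences and needs no new patients or assays, since the McNemar tables already presume biopsy and surgical scores in both groups. One lead marker loses no power to multiplicity. Holm costs up to 11 points for the paired test (88% to 77%) or 17 for the between-group change (60% to 43%) at its strictest step, under the assumptions above.

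The choice of contrast has its own price. With the same SD and 50 per group, making the between-group change decisive lowers power from 88% to 60% before any adjustment. The paired test keeps that power but cannot separate a drug effect from a systematic biopsy-to-surgery difference. The plan should give the SD, the control-group size and the resulting power for whichever contrast it names.
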